4.3.2. Study Treatment Groups Presentation

The summary of study data will include all relevant data obtained throughout a specific study period for the following respective patient groups. The grouping of patients for efficacy and safety data will be primarily based on the randomized treatment and the actual treatment received in Part 1, respectively, and whether patients received at least one dose of open-label ABSK021 beyond Part 1. The groups included in a specific table, figure, and listing (TFL) depend on their primary purpose and analysis stages.

Statistical Analysis Plan for Protocol ABSK-021-301

Table 4.6 Efficacy Data Display of Study Treatment Groups

Part	SAP		CSR Report	
	Description	Data inclusion	TFL Display (Order)	Included in Analysis
Part 1	Randomized Placebo in Part 1	Data from patients who were randomized to Placebo during Part 1 before their first dose in Part 2	Placebo P1 (1)	Primary analysis* Final analysis*
	Randomized ABSK021 in Part 1	Data from patients who were randomized to ABSK021 during Part 1 before their first dose in Part 2.	ABSK021 P1 (2)	Primary analysis Final analysis
Part 2 and Part 3	Placebo Switch to ABSK021	Part 2 and Part 3 data from patients who switched from blinded Placebo to open-label ABSK021 in Part 2	Switched to ABSK021 P2+P3 (3)	Primary analysis Final analysis
Part 1, 2 and Part 3	Randomized ABSK021 with longer follow up	Parts 1- 3 data up to the DCO from the patients who were randomized to ABSK021 in Part 1	ABSK021 P1-P3 (4)	Primary analysis Final analysis
Part 1, 2 and Part 3	All ABSK021 Treated	Parts 1-3 data up to the DCO from patients who received at least 1 dose of ABSK021	All ABSK021 Treated P1-P3 (5)	Primary analysis Final analysis End of study analysis

*Note: the primary and final analyses are defined in [Section 2](#).

Statistical Analysis Plan for Protocol ABSK-021-301

Table 4.7 Safety Data Display of Study Treatment Groups

Part	SAP		CSR Report	
	Description	Data inclusion	TFL Display (Order)	Included in Analysis
Part 1	Received Placebo in Part 1	Data from the patients who received blinded Placebo during Part 1 before their first dose in Part 2	Placebo P1 (1)	Primary analysis* Final analysis*
Part 1	Received ABSK021 in Part 1	Data from the patients who received blinded ABSK021 in Part 1 before their first dose in Part 2	ABSK021 P1 (2)	Primary analysis Final analysis
Part 2 and Part 3	Placebo Switch to ABSK021	Part 2 and Part 3 data from patients who switched from blinded Placebo to open-label ABSK021 in Part 2	Switched to ABSK021 P2+P3 (3)	Primary analysis Final analysis
Part 1, 2 and Part 3	Received ABSK021 with longer follow up	Parts 1- 3 data up to the DCO from the patients who received blinded ABSK021 in Part 1	ABSK021 P1-P3 (4)	Primary analysis Final analysis
Part 1, 2 and Part 3	All ABSK021 Treated	Parts 1-3 data up to the DCO from patients who received at least 1 dose of ABSK021	All ABSK021 Treated P1-P3 (5)	Primary analysis Final Analysis End of study analysis

*Note: the primary and final analyses are defined in [Section 2](#).

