7.4.7.1 Treatment-emergent Adverse Events (TEAEs)

A treatment-emergent adverse event (TEAE) is defined as any adverse event that occurs or worsens after the initiation of treatment in this study until 30 days after the last dose of the study drug. Adverse event (AE) data will be coded to system organ class (SOC) and preferred term (PT) using the most recent version of MedDRA. The severity of AEs (toxicity grade 1-5) will be graded by the Investigator according to NCI-CTCAE version 5.0. Any treatment-emergent adverse events, study treatment-related adverse events, adverse events leading to discontinuation of study drug, adverse events leading to dose modification, serious adverse events, etc., will be summarized by SOC, PT, and CTCAE version 5.0 grade.

The summary of TEAEs will be performed for the following groups:

- 1) For patients who received ABSK021 in Part 1, include Part 1 data only.
- 2) For patients who received placebo in Part 1, include Part 1 data only.
- 3) For patients who received ABSK021 in Part 1 and Part 2, include Part 1 and Part 2 data for these patients.
- 4) For patients who received placebo in Part 1 and treated with ABSK021 in Part 2, include Part 2 data only.
- 5) For all patients who received at least one dose of ABSK021 in Part 1 and/or Part 2, include the data on ABSK021 treatment in Part 1 and Part 2, and exclude the data on placebo treatment in Part 1.
- 6) For all patients who received at least one dose of ABSK021 in Part1, Part 2 and/or Part 3, include the data on ABSK021 treatment form Part 1 to Part 3, and exclude the data on placebo treatment in Part 1.

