4.2.3. Study Day and Duration

Where appropriate, the calculated study day or duration of each assessment or event will be presented with the assessment or event date on patient data listings, where study day will be determined as:

- If the assessment/event date < the reference start date, then
Study Day = event start date (visit date, onset date, assessment date) - reference start date
- If the assessment/event date \geq the reference start date, then
Study Day/Duration = event start date (visit date, onset date, assessment date) - reference start date + 1

Table 4.1 Reference start date for efficacy and safety data

	Study Part 1		Study Part 2 and 3	
	Efficacy	Safety	Efficacy	Safety
Patients randomized to ABSK021	Randomization date	First Part 1 dose	Randomization date	First Part 1 dose
Patient randomized to Placebo and switched to ABSK021	Randomization date	First Part 1 dose	First Part 2 dose	First Part 2 dose

The study day will be displayed in data listings along with the start dates of the event and reference.

The following unit conversion factor will be used to present duration in week, month or year.

- Weeks: A duration expressed in weeks will be calculated by dividing the duration in days by 7
- Months: A duration expressed in months will be calculated by dividing the duration in days by 30.4375
- Years: A duration expressed in years will be calculated by dividing the duration in days by 365.25

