4.2.4. Definition of Analysis Windows

The window for the visits following baseline will be constructed in such a way that the upper limit of the interval falls halfway between the two visits (the lower limit of the first post-baseline

Statistical Analysis Plan for Protocol ABSK-021-301

visit will be Day 2). If an even number of days exists between two consecutive visits then the upper limit will be taken as the midpoint value minus 1 day.

The following rules will be applied to assign actual patient visits to protocol-specified visits. For each protocol-specified study visit, a target study day will be identified to represent the corresponding visit along with a window around the target day. Windows will be selected in a non-overlapping fashion so that a collection date does not fall into multiple visit windows. If a patient has two or more actual visits in one visit window, the visit closest to the target day will be used for analysis. If two visits are equidistant from the target day, then the later visit will be used for analysis.

The visit window and the target study day from Part 1 for each protocol-specified visit are displayed in [Table 4.2](#) and [Table 4.3](#) (depending on the different visit schedules of different endpoints).

Table 4.2 Analysis Windows for PRO endpoints and Range of Motion

Study Period	Protocol Specified Visit	Target Day	Visit Window Range [min, max]		
			Worst Stiffness NRS, BPI Worst Pain NRS, PROMIS-PF and EQ-5D-5L	Range of Motion	NCI-PRO-CTCAE
Part 1	Baseline	1[a]	[-28, 1]	[-28, 1]	[-28, 1]
	Week 2 (C1D8)	8			[2,11]
	Week 3 (C1D15)	15			[12, 18]
	Week 4 (C1D22)	22			[19,25]
	Week 5 (C2D1)	29	[2, 43]		[26, 32]
	Week 6 (C2D8)	36			[33,39]
	Week 7 (C2D15)	43			[40, 46]
	Week 8 (C2D22)	50			[47, 53]

Statistical Analysis Plan for Protocol ABSK-021-301

Study Period	Protocol Specified Visit	Target Day	Visit Window Range [min, max]		
			Worst Stiffness NRS, BPI Worst Pain NRS, PROMIS-PF and EQ-5D-5L	Range of Motion	NCI-PRO-CTCAE
	Week 9 (C3D1)	57	[44, 71]		[54, 71]
	Week 13 (C4D1)	85	[72, 99]	[2, 127]	[72, 99]
	Week 17 (C5D1)	113	[100, 127]		[100, 127]
	Week 21 (C6D1)	141	[128, 155]		[128, 155]
	Week 25 (C7D1)	169	[156, 1st dose date of Part 2 or 184]	[128, 1st dose date of Part 2 or 184]	[156, 1st dose date of Part 2 or 184]
Part 2	Week 25 (C1D1)[b]	169	[156, 1st dose date of Part2]		
	Week 29 (C2D1)	197	[1 day after 1st dose date of Part 2, 211]		
	Week 33 (C3D1)	225	[212, 239]		

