	Week 49 (C7D1)	337	[296, 1st dose date of Part 3 or 352]	[296, 1st dose date of Part 3 or 352]	[296, 1st dose date of Part 3 or 352]	[296, 1st dose date of Part 3 or 352]
Part 3	Week 61 (C4D1)	421	[1 day after 1st dose date of Part 3, 463]	[1 day after 1st dose date of Part 3, 463]	[1 day after 1st dose date of Part 3, 463]	[1 day after 1st dose date of Part 3, 463]
	Week 73 (C7D1)	505	[464, 548]	[464, 548]	[464, 548]	[464, 548]
	Week 97 (C13D1)	673	[549, 757]	[549, 757]	[549, 757]	[549, 757]

Statistical Analysis Plan for Protocol ABSK-021-301

Study Period	Protocol Specified Visit	Target Day	Visit Window Range [min, max]			
			Pregnancy test	Hematology / Urinalysis / Physical examination / ECOG	Blood chemistry / Myocardial Enzyme Test / Vital Signs / 12-lead ECG	Coagulation / Thyroid function tests / Echocardiography/MUGA
	Week 121	841	[758, 925]	[758, 925]	[758, 925]	[758, 925]
	+ 24 weeks					

- a. Day of first dose of study drug.
b. Part 2 baseline for placebo arm in Part 1.

If a patient early discontinues from Part 1 and directly enters into Part 2, the following visit window in Part 2 and Part 3 will be recalculated based on the new target study day from Part 2 and displayed in [Table 4.4](#) and [Table 4.5](#) as below.

Table 4.4 Early entering Part 2 Analysis Windows for PRO endpoints and Range of Motion

Study Period	Protocol Specified Visit	Target Day	Visit Window Range [min, max]	
			Worst Stiffness NRS, BPI Worst Pain NRS, PROMIS-PF and EQ-5D-5L	Range of Motion
Part 2	Week 25 (C1D1)[a]	1	[-14, 1]	
	Week 29 (C2D1)	29	[2, 43]	
	Week 33 (C3D1)	57	[44, 71]	
	Week 37 (C4D1)	85	[72, 127]	[2, 127]
	Week 49 (C7D1)	169	[128, 1st dose date of Part 3 or 184]	[128, 1st dose date of Part 3 or 184]

Statistical Analysis Plan for Protocol ABSK-021-301

Study Period	Protocol Specified Visit	Target Day	Visit Window Range [min, max]	
			Worst Stiffness NRS, BPI Worst Pain NRS, PROMIS-PF and EQ-5D-5L	Range of Motion
Part 3	Week 61 (C4D1)	253	[1st dose date of Part 3 +1, 295]	[1st dose date of Part 3 +1, 295]
	Week 73 (C7D1)	337	[296, 380]	[296, 380]
	Week 97 (C13D1)	505	[381, 589]	[381, 589]
	Week 121	673	[590, 757]	[590, 757]
	+ 24 weeks			

a. Day of first dose of Part 2

Table 4.5 Early entering Part 2 Analysis Windows for Safety Endpoints

Study Period	Protocol Specified Visit	Target Day	Visit Window Range [min, max]			

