9. CHANGE FROM ANALYSIS PLANNED IN PROTOCOL

Plan specified in protocol	Change in SAP and rationales
NA	NA

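### The SAP's pooled ABSK021 safety column takes in switchers' placebo period, and its Part 2/3 visit windows rest on two unreconciled day scales

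*SAP*

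**What the plan says.** **Pooled column.** Row 5 of SAP Table 4.7 (Section 4.3.2) takes in "Parts 1-3 data up to the DCO from patients who received at least 1 dose of ABSK021". Row 3 of the same table, for switchers alone, is limited by study part: "Part 2 and Part 3 data from patients who switched from blinded Placebo to open-label ABSK021 in Part 2". Row 5 has no such limit. Table 4.6 repeats row 5 for efficacy.

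Protocol 7.4.7.1 defines the matching pools as its groups 5 and 6. For group 5 the instruction is to "include the data on ABSK021 treatment in Part 1 and Part 2, and exclude the data on placebo treatment in Part 1"; group 6 extends the same rule to Part 3. SAP 7.1 starts the on-treatment period at the first dose of study drug, without naming ABSK021. In SAP Section 9 the column headed "Plan specified in protocol" holds only NA.

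**Visit windows.** In SAP Table 4.1 the row "Patient randomized to Placebo and switched to ABSK021" gives the first Part 2 dose as the reference date for Parts 2 and 3, for both efficacy and safety. SAP 4.2.4 describes the target days of Tables 4.2 and 4.3 as coming from Part 1; for Part 2 Weeks 29, 33, 37 and 49 they are 197, 225, 253 and 337. The Week 29 PRO window reads "1 day after 1st dose date of Part 2, 211": its lower limit is a Part 2 date and its upper limit a Part 1 day number. Footnote b places the placebo arm in these tables. Tables 4.4 and 4.5 restart the count at the first Part 2 dose, but their stated scope is "If a patient early discontinues from Part 1 and directly enters into Part 2". The footnotes to the protocol's Part 1 schedule allow, in principle, up to 28 days between the end of the Part 1 C7D1 follow-up and entry into Part 2.

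**The concern.** Row 5 selects patients, not treatment periods. Once a switcher takes one ABSK021 dose, the Part 1 placebo events and time enter a column whose title says ABSK021. That column appears at the primary, final and end-of-study analyses, and it is the only Table 4.7 group listed for the last of these. SAP 5.6 also applies the Table 4.7 groups to drug exposure. A programmer following the SAP and one following the protocol would therefore produce different tables, with no declared change to explain the difference.

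The window tables raise a similar problem for by-visit summaries beyond Part 1. The SAP does not say which day number goes into Tables 4.2 and 4.3 for a switcher. The fixed Part 1 day numbers also leave limited room for the delay that the protocol permits before Part 2. Values could then be reported under the wrong week or lost.

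**Working it through.** **The plan's own figures.** Counted from Part 1 Day 1, target day = (week − 1) × 7 + 1. This gives 197, 225, 253 and 337, as in Table 4.2. The upper limits are midpoints of consecutive targets: (197 + 225)/2 = 211, (225 + 253)/2 = 239, (253 + 337)/2 = 295. These match. Table 4.4 reproduces as (week − 25) × 7 + 1 = 29, 57, 85, 169, counted from the first Part 2 dose.

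**Person-time in row 5.** Inputs: 60 ABSK021 and 30 placebo patients (Protocol 4.1); Parts 1 and 2 of 24 weeks = 168 days each (Protocol 5.4). Assume that everyone completes both parts, all 30 switch and no Part 3 time is counted.

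- Placebo time added: 30 × 168/365.25 = 13.8 patient-years.
- True ABSK021 time through Week 49: (60 × 336 + 30 × 168)/365.25 = 69.0.
- Row 5 as written: 69.0 + 13.8 = 82.8. Placebo share: 13.8/82.8 = 16.7%.

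The share depends on how much ABSK021 time has accrued. If all 90 patients had 12 weeks of Part 2 (an assumption), ABSK021 time would be (60 × 252 + 30 × 84)/365.25 = 48.3, and the share 13.8/62.1 = 22%. Part 3 time lowers it.

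**Direction of the effect.** SAP 7.2.4 divides crude TEAE counts by the number of patients in the group. Switchers are in row 5 with or without their placebo data, so the denominator is fixed and extra events can only raise the count or leave it unchanged. The exposure-adjusted rate in the overview table takes in extra events and extra time, and its date of first exposure does not say to which drug. It can move either way, depending on how frequent the event is on placebo.

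**Windows with Table 4.1 days.** A switcher's Part 2 PRO visits fall on Days 29, 57, 85 and 169. The Week 29 window becomes [2, 211] and holds all four. Distances to target 197 are 168, 140, 112 and 28, so the closest-to-target rule keeps Day 169. The Week 49 value is reported as Week 29, and none of the four visits reaches the Week 33, 37 or 49 windows.

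**Windows with Part 1 days.** Take Part 1 C7D1 on Day 169, a gap of g days to the first Part 2 dose, and nominal Part 2 visits. C2D1, C3D1, C4D1 and C7D1 then fall on Days 197 + g, 225 + g, 253 + g and 337 + g. The windows are Week 33 [212, 239], Week 37 [240, 295], and Week 49 from 296 to the first Part 3 dose or Day 352.

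| g | C2D1 | C3D1 | C4D1 | C7D1 |
|---|---|---|---|---|
| 0 | 197, Week 29 | 225, Week 33 | 253, Week 37 | 337, Week 49 |
| 14 | 211, Week 29 | 239, Week 33 | 267, Week 37 | 351, Week 49 |
| 15 | 212, Week 33 | 240, Week 37 | 268, displaced | 352, Week 49 |
| 16 | 213, Week 33 | 241, Week 37 | 269, displaced | 353, past Day 352 |
| 28 | 225, Week 33 | 253, Week 37 | 281, displaced | 365, past Day 352 |

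C4D1 is displaced because C3D1 lies 28 − g days from target 253 and C4D1 lies g days from it, so C3D1 is closer whenever g exceeds 14. C7D1 passes Day 352 from g = 16 unless Part 3 entry extends the window.

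The relabelling applies to endpoints with Week 29 and 33 windows: the PRO scores, haematology, urinalysis, physical examination, ECOG, chemistry, myocardial enzymes, vital signs and ECG. ROM, coagulation, thyroid tests, echocardiography and pregnancy tests have no Week 29 or 33 window, and their C4D1 stays in Week 37 (Day 281 against a limit of 295). For them only the C7D1 limit matters.

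**The case against.** The best defence of row 5 is intent. The column is titled as ABSK021-treated, SAP 4.2.2.3 and 7.1 reset switchers' baseline before the first Part 2 dose, and Table 4.1 resets their reference date. For efficacy the SAP goes further: Section 6.1 derives switchers' post-baseline values only from data after the first Part 2 dose. That answers the point for efficacy values, so Table 4.6 needs only aligned wording. The protocol's exclusion also concerns TEAE summaries, so a reader who infers a protocol conflict in the efficacy table goes beyond the text. For safety, a reset baseline is evidence of intent, not an exclusion of events or exposure time, and no SAP sentence excludes them.

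On windows, SAP 4.2.3 introduces study day for listings and 4.2.4 states its own Part 1 scale, so Part 1 days may well be what is meant. That reading would remove the Table 4.1 problem, but the SAP does not state it, and the gap problem remains. Long gaps may be uncommon: the 28 days is a maximum, and Part 2 drug may be dispensed on the day Part 1 C7D1 is completed. The documents do not allow their frequency to be estimated.

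A reader might infer that a switcher's Part 2 C2D1, at Day 29, would land in the Part 1 Week 5 window. It would not: the tables are split by study part, and the Week 29 window opens the day after the first Part 2 dose.

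**Conclusion.** Both parts hold. Row 5 of Table 4.7 contradicts Protocol 7.4.7.1 without a declared change. It adds at most 13.8 placebo patient-years, about 17% of the pooled time through Week 49 under full completion, full switching and no Part 3 time. The window tables are ambiguous for switchers. On the Part 1 scale they mislabel Part 2 visits for gaps of 15 to 28 days, in either arm, assuming nominal visit dates.

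Three stronger conclusions are not supported:

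- That the pooled safety rates are diluted throughout. Crude incidence can only rise or stay the same; dilution is possible only in exposure-adjusted rates, for events less frequent on placebo.
- That placebo could make up a third of the pool. That needs 13.8/(13.8 + 27.6), with all 30 switchers included and no Part 2 time for anyone, yet a switcher enters the pool only by taking a Part 2 dose.
- That the trial's main conclusions are at risk. The Part 1 primary and key secondary tests do not use row 5 or the Part 2/3 windows, and tumour response is not assigned by these tables.

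This should be corrected because two analysts could follow the plan and report different safety and long-term by-visit results.

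**What to change.** 1. Reword row 5 of Table 4.7: data from the first dose of ABSK021 (Part 1 if received in Part 1, Part 2 if switched) to the data cut-off, excluding data on placebo treatment in Part 1.
2. State that, for this group, first dose and first exposure mean the first ABSK021 dose in the exposure, on-treatment and exposure-adjusted rate definitions.
3. Align row 5 of Table 4.6 with SAP 6.1.
4. Window the Part 2/3 visits of all patients from the first Part 2 dose, using Tables 4.4 and 4.5. Nominal Part 2 visits then fall in their own windows whatever the gap before Part 2. A gap of 28 days before Part 3 is also absorbed at the first two Part 3 visits: Week 61 moves from Day 253 to 281 (limit 295) and Week 73 from 337 to 365 (limit 380).
5. Add to Table 4.1 that this window day is separate from the study-day reference, which stays at randomisation or the first Part 1 dose for patients randomised to ABSK021. Without that sentence, step 4 would create a new conflict.

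The cost is SAP wording and programming. The re-based tables already exist, and no new data or design change is needed.

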5. BACKGROUND CHARACTERISTICS

5.1. Patient Disposition

The patient disposition summary will include the following groups:

Statistical Analysis Plan for Protocol ABSK-021-301

- Screened patients: the total number of screened patients by overall will be presented for the following groups: screened, screening failure and primary reasons for screening failure.
- Enrolled patients: the total number of enrolled patients by overall will be presented for the following groups: enrolled patients (i.e., signed informed consent form and meet eligible criteria), enrolled but not randomized and primary reasons.
- Randomized patients: the total number of randomized patients by randomized treatment group and overall will be presented for the following groups: randomized patients, randomized but not received treatment and primary reasons.
- Patients entered Part 1: the total number and percentage of patients by randomized treatment group and overall will be presented for the following groups: received treatment, treatment completed, treatment discontinuation and the primary reasons, completed Part 1 study completed, early withdrawal from the study Part 1.
- Patients entered Part 2: the total number and percentage of patients by randomized treatment group and overall will be presented for the following groups: entered Part 2, not enter Part 2 and primary reasons, received treatment, treatment completed, treatment ongoing, treatment discontinuation and the primary reasons, Part 2 study completed, study ongoing, early withdrawal from the study Part 2.
- Patients entered Part 3: the total number and percentage of patients by randomized treatment group and overall will be presented for the following groups: entered Part 3, not enter Part 3 and primary reasons, received treatment, treatment completed, treatment ongoing, treatment discontinuation and the primary reasons, Part 3 study completed, early withdrawal from the study Part 3.

All these primary reasons for premature treatment and study discontinuations will be based on data collected from the end of treatment and the end of study CRF pages for each study part. The denominators for calculating all percentages will be the number of patients who received the study drug in each randomized treatment group within each study part.

The total number and percentage of patients by randomized treatment group and overall will be presented for analysis data sets (excluding screened set), including those patients who were excluded from any analysis set and primary reasons for exclusion, if applicable.

Patient eligibility information (including Initial Informed Consent Date, Protocol Version Number, Additional Optional Informed Consent Date, Eligibility criteria not met) will be listed for all screened patients.

Patient recruitment by region (China, US/North America, EU), country, and center will be summarized by randomized treatment based on ITT analysis set. Randomization details will be listed, including the data of randomization, randomization number and randomization strata, and any prematurely unblinding, date and reasons for early unblinding prior to completion of Part 1 treatment.

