Clinical laboratory tests								
Pregnancy test ⁸	X			X	X	X		
Hematology ⁹	X	X	X	X	X	X		
Blood chemistry ¹⁰	X	X	X	X	X	X		
Myocardial Enzyme Test ¹¹	X	X	X	X	X	X		
Coagulation ¹²				X	X	X		
Urinalysis ¹³	X	X	X	X	X	X		
Thyroid function tests ¹⁴				X	X	X		
12-lead ECG ¹⁵	X	X	X	X	X	X		

Study Procedure	Cycle/Day	Cycle 1 ¹	Cycle 2	Cycle 3	Cycle 4 ²	Cycle 7	End of Treatment Visit (EOT Visit) ³	Safety Follow-up ⁴	Progression Follow-up ⁵
		C1D1 (- 2 days)	C2D1 (± 7 days)	C3D1 (± 7 days)	C4D1 (± 7 days)	C7D1 (± 7 days)			
		Week 25	Week 29	Week 33	Week 37	Week 49			
Echocardiography/MUGA ¹⁶		X			X	X	X		
Adverse Event Reporting ¹⁷		X	X	X	X	X	X	X	
Concomitant Medications and Concomitant Therapies ¹⁸		X	X	X	X	X	X	X	
Dispensing of ABSK021 ¹⁹		X	X	X	X				
PK Sample Collection ²⁰					X	X	X		
Tumor Imaging Assessment ²¹					X	X	X		X
ROM of affected joints ²²					X	X	X		
Worst Stiffness NRS and BPI Worst Pain NRS ²³		X	X	X	X	X	X		
PROMIS Physical Functioning Scale ²⁴		X	X	X	X	X	X		
EQ-5D-5L Health Scale ²⁴		X	X	X	X	X	X		
Pre-Part 3 Evaluation ²⁵						X			
New anti-tumor therapy after discontinuation of study drug								X	X

Abbreviations: ALT= Alanine transaminase; AST= Aspartate transaminase; APTT= activated partial thromboplastin time; BUN= Blood urea nitrogen; CK= creatine phosphokinase; CK-MB= phosphocreatine kinase isoenzyme; ECG= electrocardiogram; ECOG= Eastern Cooperative Oncology Group; EOT= End-of-Treatment; Fbg=fibrinogen; LDH= lactate dehydrogenase; MRI=

magnetic resonance imaging; MUGA= multigated acquisition scans; PK= Pharmacokinetic; PS= Performance status; TSH= Thyroid stimulating hormone; FT3= Free triiodothyronine; FT4= Free Thyroxine; WBC= white blood cells.

Footnote:

Additional unscheduled safety or efficacy assessments may be performed as clinically indicated to determine the relationship between events and/or the duration of the event. All time windows in the table are for visits and not for administration.

1. C1D1 of Part 2 (P2-C1D1) is defined as the day of Part 2 eligibility confirmation and the first dose of Part 2, and if any test to be performed at Part 2 C1D1 visit has been done at Part 1 C7D1 visit or the latest visit before Part 2 C1D1, with an interval no more than 7 days, repeated tests are not required on C1D1 of Part 2.
2. After completing the Cycle 4 (i.e., Week 37) visit of Part 2, patients will return to the study site for a visit every 12 weeks (± 7 days) with the next visit date of C7D1 ± 7 days.

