1.3. Sample Size Consideration

The sample size of this study is calculated based on the primary objective of the study, which is to compare the objective response rate within 25 weeks after treatment with ABSK021 or placebo in TGCT patients.

The target ORR of 40% for ABSK021-301 was anticipated from this study (i.e., 85% of the lower limit of 95% CI for interim ORR in ABSK021-101) based on the following considerations: a) Limited sample size in ABSK021-101 interim analysis; b) The inclusion of TGCT patients in the Phase 3 study will be more stringent than ABSK021-101 study which could lead to the enrolment of patients with a more severe condition. This may have a detrimental influence on treatment effectiveness; c) A single region preliminary ORR results from ABSK021-101 may not completely reflect the true response from the multi-region trial in a placebo control study.

Patients will be randomized in a 2:1 ratio to ABSK021 treatment group or placebo group. Assuming a 25-week ORR of 6% (P_0) (the upper 95% CI of the placebo group in the ENLIVEN¹ study) in the placebo group and 40% (P_1) for ABSK021, by using Fisher's exact test with a two-sided significance level α of 0.05, a sample size of 75 evaluable patients provides a 90% power to detect the difference in the ORR between the two groups ($H_0: P_1 = P_0$ vs. $H_a: P_1 \neq P_0$). The power is calculated using the binomial distribution enumeration method (PASS 2021, v21.0.3). Considering a dropout rate of about 15%, approximately 90 TGCT patients need to be enrolled, including 60 patients in the ABSK021 treatment group and 30 patients in the placebo group.

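### SAP 5.1 divides the entered and not-entered rows for Parts 2 and 3 by patients dosed in that same Part, so non-entry is overstated and entry is normally fixed at 100%

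*SAP*

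**What the plan says.** SAP 5.1 (Patient Disposition) builds the table in blocks. The Part 2 block is to show counts and percentages: "Patients entered Part 2: the total number and percentage of patients by randomized treatment group and overall will be presented". Its rows begin "entered Part 2, not enter Part 2 and primary reasons, received treatment, treatment completed, treatment ongoing". The Part 3 block has the same structure: "entered Part 3, not enter Part 3 and primary reasons, received treatment, treatment completed, treatment ongoing".

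A single closing sentence then fixes the denominator: "The denominators for calculating all percentages will be the number of patients who received the study drug in each randomized treatment group". The sentence goes on to make the count specific to each Part: "who received the study drug in each randomized treatment group within each study part". The section gives no separate denominator for the entry rows.

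Nothing else in the documents supplies one. Protocol 7.4.2 lists the disposition items without denominators, and the table of changes in SAP 9 is marked NA. SAP 4.3.1 refers to a separate file of table mock-ups, which is not among the documents.

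**The concern.** The denominator suits rows that describe what happened on treatment within a Part: completed, ongoing, discontinued. It does not suit rows that describe whether a patient got into the Part. Non-entrants to Part 2 receive no Part 2 drug, so they are counted in the numerator and left out of the denominator. The entered row, in turn, is divided by practically the same patients it counts, so it says nothing about retention.

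At stake is how well a reader can judge carry-over from the randomized phase. The long-term response summaries (SAP 6.6.1) and the longer-follow-up safety groups (SAP Table 4.7) depend on who continued. Retention by randomized arm, with reasons, is the natural check on that selection. Because the distortion grows with attrition, it is larger in whichever arm loses more patients.

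**Working it through.** The documents state no disposition percentage, so there is no figure to reproduce. The check applies the SAP rule to illustrative counts.

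**Inputs**
- Rule: all percentages are divided by patients dosed within the Part (SAP 5.1).
- Entry and dosing: Part 2 Cycle 1 Day 1 "is defined as the day of Part 2 eligibility confirmation and the first dose of Part 2" (Protocol Table 2, footnote 1). Table 3, footnote 1 likewise ties Part 3 Cycle 1 Day 1 to the first Part 3 dose. Entered and dosed therefore normally coincide.
- Arm sizes: "including 60 patients in the ABSK021 treatment group and 30 patients in the placebo group" (SAP 1.3). I assume that every randomized patient is dosed in Part 1.
- Non-entry shares: assumed, because the documents forecast none.

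**Formulas.** Let N be the patients dosed in the preceding Part, m those who do not enter the next Part, and E = N − m those who enter and are dosed, with nobody pending.
- SAP rule: not entered = m/E; entered = E/E.
- Preceding-Part denominator: not entered = m/N; entered = E/N.
- Overstatement of non-entry: (m/E)/(m/N) = N/E = 1/(1 − m/N).

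**Part 2 entry, ABSK021 arm, N = 60**

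| m | E | Not entered, m/N | Not entered, SAP rule | Entered, E/N | Entered, SAP rule |
|---|---|---|---|---|---|
| 3 | 57 | 3/60 = 5.0% | 3/57 = 5.3% | 95.0% | 100% |
| 9 | 51 | 9/60 = 15.0% | 9/51 = 17.6% | 85.0% | 100% |
| 15 | 45 | 15/60 = 25.0% | 15/45 = 33.3% | 75.0% | 100% |

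In the middle row the two SAP percentages add to 117.6%; with the preceding-Part denominator they add to 100%.

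**Part 2 entry, placebo arm, N = 30, m = 4.** Not entered is 4/30 = 13.3%, reported as 4/26 = 15.4%. Entered is 26/30 = 86.7%, reported as 100%.

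**Part 3 entry.** Suppose 51 patients are dosed in Part 2 and 43 in Part 3. Not entered is 8/51 = 15.7%, reported as 8/43 = 18.6%.

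**Patients still in the preceding Part.** The primary analysis cuts data at the last patient's Week 25 visit (SAP 2.1), when others may still be in Part 2. Assume 51 dosed in Part 2, of whom 20 have been dosed in Part 3, 5 have stopped without entering, and 51 − 20 − 5 = 26 are undecided. The SAP rule gives 5/20 = 25.0% not entered. Divided by 51, the figures are 39.2% entered, 9.8% not entered and 51.0% pending, which add to 100%. The simple factor above applies only when nobody is pending; in general the ratio is N/E, here 51/20 = 2.55.

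**The case against.** The best defence is that the denominator sentence directly follows one about reasons for stopping treatment or leaving the study. For those rows a within-Part treated denominator is sound, so one might read the rule as confined to them. The wording covers all percentages, however, and no other denominator is offered. A programmer might notice the oddity, but one who follows the text would produce the wrong table.

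The other objections limit how far the point goes, and they stand:

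- **Impact.** Counts are printed beside the percentages, so a reader can recover the right proportion. SAP 6.4.2 separately plans the percentage discontinuing or withdrawing by arm, with Kaplan-Meier plots. A reader might infer that the long-term response or safety results are themselves wrong. They are not: no estimate, analysis set or test uses this denominator.
- **Entry above 100%.** A reader might infer that the entered row will exceed 100%. That needs a patient recorded as entered but never dosed (51/50 = 102.0%, for example). Since the first dose defines Day 1 of each Part, the normal result is exactly 100%.
- **The 15% figure.** A reader might take the 15% dropout in SAP 1.3 as the plan's forecast of non-entry. It is an allowance that raises 75 evaluable patients to about 90. Part 1 completers may simply end treatment (Protocol Table 1, footnote 2), and some patients with progression may enter Part 2 early (Protocol 4.3.1).
- **The Part 1 block.** A reader might extend the criticism there. That block has no not-entered row. A treated denominator makes its received-treatment row trivially 100%, which is uninformative but not wrong.

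**Conclusion.** The point holds for four rows: entered and not entered, for Part 2 and for Part 3. Followed as written, SAP 5.1 reports an odds as a percentage of non-entrants and a near-constant 100% for entrants. This is a rule stated too broadly, not a miscalculated number.

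The size depends on attrition, which is unknown. Over an assumed 5% to 25% non-entry, the relative overstatement runs from 1/0.95 = 1.05 to 1/0.75 = 1.33, provided that entered and dosed coincide and nobody is pending at the cut-off. With no non-entrants and nobody pending, there is no error. The consequence is confined to descriptive disposition reporting, so this is a minor correction worth making before the tables are programmed.

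**What to change.** In SAP 5.1, limit the existing denominator sentence and add one for the entry rows:

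- Entered and not entered Part 2, with reasons: divide by patients treated in Part 1, by randomized group.
- Entered and not entered Part 3, with reasons: divide by patients treated in Part 2, by randomized group.
- Add a row to each block for patients still in the preceding Part or with entry pending at the data cut-off, so that the three rows add to 100%. Besides patients still on treatment, the protocol allows in principle up to 28 days between the last visit of one Part and entry to the next (Table 1, footnote 30; Table 2, footnote 25).
- Keep patients treated within the Part as the denominator for treatment completed, ongoing and discontinued.

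Use patients treated in the preceding Part, not those who completed it; a base of Part 1 completers would leave out patients who move to Part 2 early after progression. The Part 1 block need not change.

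The cost is a sentence or two in the SAP, one extra table row per block, and a denominator change in the disposition program. No new data are needed beyond entry status at the cut-off.
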